4.6.3 Adjudicated Anaphylactic and Hypersensitivity Reactions

Anaphylaxis and hypersensitivity events as adjudicated by the Anaphylaxis Adjudication Committee will be summarized descriptively. Listing of treatment emergent adverse events of anaphylaxis and hypersensitivity as defined above and their assessment by an Independent Anaphylaxis Adjudication Committee as per the Anaphylaxis Adjudication Committee charter will be produced.

4.6.4 Laboratory Data

Descriptive summaries of laboratory values at baseline, by visit, and change from baseline throughout the study will be tabulated by each treatment arm. Highest NCI CTCAE v.5.0 grade post-baseline will also be reported and shift tables from baseline to worst value during the study post-baseline will be presented by each treatment arm.

Summaries will be analyzed for the following parameters: hematology (hemoglobin, hematocrit, platelet count, RBC count, WBC count, and differential counts [lymphocytes, eosinophils, neutrophils, monocytes, and basophils]), serum chemistries and liver function tests (LFTs) (sodium, potassium, chloride, bicarbonate, glucose, blood urea nitrogen, creatinine, calcium, total and direct bilirubin, total protein, albumin, alanine aminotransferase, aspartate aminotransferase, alkaline phosphatase, C-reactive protein [CRP], eGFR) and urinalysis (pH, specific gravity, glucose, protein, ketones, blood, sediment, RBCs, WBCs, casts, crystals, epithelial cells, bacteria).

Proportion of patients experiencing clinically significant changes relative to baseline will be summarized by treatment arm as appropriate for the parameters listed above.

A Hy’s law analysis will be provided. The potential Hy’s law quadrant is defined as ALT or AST increases above 3-fold the upper limit of normal (ULN) with concomitant total bilirubin increases above 2-fold the ULN or clinical jaundice in the absence of cholestasis or other causes of hyperbilirubinemia is considered as an indicator of severe liver injury (as defined by Hy’s Law).

Visual plots (box plots or line plots) will be used to display selected laboratory parameters over time/by visit where appropriate.

4.6.5 Vital Signs

Values, along with change from baseline, will be summarized using descriptive statistics for each vital sign parameter.

Summary statistics on absolute values and their change from baseline for all observed vital signs (respiratory rate, pulse rate, systolic and diastolic blood pressure while the patient is in a seated position, oxygen saturations, and temperature) will be presented over time by treatment group. Baseline is defined as the last assessment prior to treatment.

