- Four infusion-related reactions (IRRs) occurred in three patients, two patients in the PRM-151 group (2.6%) and one patient in the placebo group (2.6%). One patient in the PRM-151 group experienced dizziness and another experienced a hypertensive crisis event; one patient in the placebo group experienced two hypertensive crisis events. There was no difference between treatment arms in the nature or frequency of IRRs. None of the IRR events was deemed serious. There were no IRR events among the seven patients with anti-drug antibodies (ADAs [six patients in the PRM-151 group; one patient in the placebo group]) through Week 28.

Risks associated with PRM-151 are inherent in it being the recombinant form of a naturally occurring human protein and consist of potential development of ADA and infusion reactions. PRM-151 has an endogenous counterpart; therefore, ADAs could develop that could potentially affect the efficacy of PRM-151 treatments in addition to having the potential to cross-react with endogenous hPTX-2.

PRM-151 is not a general immunosuppressant, and treatment with PRM-151 is not expected to increase rates of infection or adversely affect wound healing. Individuals who have chronic medical issues may be at higher risk for serious illness from COVID-19, including those with pulmonary fibrosis. However as stated above, it is not anticipated that PRM-151 will increase the risk of infection with SARS-CoV-2 or the severity of infection. *Based on the mechanism of action of PRM-151, a possible interaction between PRM-151 treatment and COVID-19 vaccination is not expected. For patients enrolling in this study and receiving PRM-151 treatment, a decision to administer the vaccine to a patient should be made on an individual basis by the investigator in consultation with the patient. When administered, COVID-19 vaccines must be given in accordance with the approved or authorized vaccine label. Receipt of the COVID-19 vaccine is considered a concomitant medication and should be documented as such (see Section 4.4.1).*

As with any protein therapeutic, the potential for reactions exists and safety procedures will be implemented, including careful monitoring of patients during infusions and of infusion sites. Appropriate personnel, medication, and other requirements for the treatment of potential infusion reactions will be required by the protocol.

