4.5.5 Vital Signs

Vital signs will include measurements of respiratory rate, pulse rate, systolic and diastolic blood pressure while the patient is in a seated position, oxygen saturations, and temperature. Record abnormalities observed at baseline on the General Medical History and Baseline Conditions eCRF. At subsequent visits, record new or worsened clinically significant abnormalities on the Adverse Event eCRF.

At dosing visits, vital signs *should* be measured predose (within 60 minutes prior to dosing), every 15 minutes during the infusion, and 30–60 minutes postdose.

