Appendix 1: Schedule of Activities

ADA=anti-drug antibody; AE=adverse event; Discon.=discontinuation; DLCO=diffusing capacity for carbon monoxide; eCRF=electronic Case Report Form; EQ-5D-5L=EuroQol 5-Dimension, 5-Level Questionnaire; HRCT=high-resolution computed tomography; IPF=idiopathic pulmonary fibrosis; OLE=open-label extension; PCR=polymerase chain reaction; PD=pharmacodynamic; PK=pharmacokinetic; SGRQ=St. George Respiratory Questionnaire; SAE=serious adverse event; SARS-CoV-2=severe acute respiratory syndrome coronavirus 2; TB=tuberculosis; Treat.=treatment, UCSD-SOBQ=University of California, San Diego-Shortness of Breath Questionnaire.

- ^a Screening period is up to 4 weeks. Eligible patients can be randomized as soon as their screening assessments have been completed and all eligibility criteria have been confirmed. Randomization must occur prior to any baseline assessments being conducted on Visit 2.
- ^b Patients will have their final safety and efficacy assessments, including HRCT if applicable, at Week 52.
- ^c Patients not enrolling in the OLE study will return for an end-of-study visit at Week 56.
- ^d Treatment discontinuation visit should occur 4 weeks after final dose of study drug. Study discontinuation visit should occur 4 weeks after the treatment discontinuation visit (8 weeks after the final dose of study drug).
- ^e To allow for flexibility around weekends, holidays, and so on, the loading dose visits may occur over a time span of up to 8 days, with a minimum of 1 full calendar day between administration of doses (patients must not be dosed on consecutive days). In case one or more loading doses have been missed or delayed beyond the 8-day loading phase window, loading doses should be administered again at the next scheduled visit. No loading doses should be administered outside of the 8-day loading phase window.
- ^f Patients who discontinue study drug early will have \pm 2-week window to complete study visits.
- ^g Testing for active or latent TB should be conducted with an interferon gamma release assay during screening. Patients who have completed treatment for active or latent tuberculosis within 6 months prior to screening, and have no evidence of recurrent disease, do not need to be tested.
- ^h On dosing days, vital signs should be completed predose (within 60 minutes prior to dosing), every 15 minutes during infusion, and 30–60 minutes postdose.

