Appendix 5 Sampson's Criteria for Diagnosing Potential Cases of Anaphylaxis

Anaphylaxis is highly likely when any one of the following three criteria is fulfilled:

- 1) Acute onset of an illness (minutes to several hours) with involvement of the skin, mucosal tissue, or both (e.g., generalized hives, pruritus or flushing, swollen lips-tongue-uvula)

AND AT LEAST ONE OF THE FOLLOWING

- a) Respiratory compromise (e.g., dyspnea, wheeze-bronchospasm, stridor, reduced peak expiratory flow [PEF], hypoxemia)
 - b) Reduced blood pressure (BP) or associated symptoms of end-organ dysfunction (e.g., hypotonia [collapse], syncope, incontinence)
- 2) Two or more of the following that occur rapidly after exposure to a likely allergen for that patient (minutes to several hours):
 - a) Involvement of the skin-mucosal tissue (e.g., generalized hives, itch-flush, swollen lips-tongue-uvula)
 - b) Respiratory compromise (e.g., dyspnea, wheeze-bronchospasm, stridor, reduced PEF, hypoxemia)
 - c) Reduced BP or associated symptoms (e.g., hypotonia [collapse], syncope, incontinence)
 - d) Persistent gastrointestinal symptoms (e.g., crampy abdominal pain, vomiting)
 - 3) Reduced BP after exposure to known allergen for that patient (minutes to several hours):
 - a) Adults: systolic BP of less than 90 mm Hg or greater than 30% decrease from that person's baseline

REFERENCE

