4.7.2 Summaries of Treatment Group Comparability

Unless otherwise specified, the baseline value for each variable will be considered the assessment collected on Baseline Day 1, prior to administration of study drug.

Demographic and baseline characteristics (including, but not limited to, age, sex, race/ethnicity, concomitant IPF medication use, comorbid illnesses, and pulmonary function) will be summarized overall for the FAS population and by treatment group using descriptive statistics as appropriate.

Compliance with study drug will be computed for each patient as the proportion of prescribed study drug actually taken for the safety population.

Proportions of patients taking each concomitant medication will be provided for the safety population.

Medical history will be summarized using summary statistics, reporting the proportion of patients with at least one medical condition and the total number of medical conditions based on the safety population.

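### SAP 4.6.5 measures vital signs against a single Day 1 baseline and specifies no within-infusion analysis of the readings taken during and after each of the 15 scheduled infusions

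*SAP*

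**What the plan says.** Protocol 4.5.5 calls for vital signs within the hour before dosing, "every 15 minutes during the infusion", and again 30–60 minutes afterwards; footnote h of Appendix 1 repeats this ("every 15 minutes during infusion, and 30–60 minutes postdose"). Protocol 4.3.2.1 schedules infusions on Days 1, 3 and 5 and then every 4 weeks to Week 48.

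Protocol 5.1 names infusion-related reactions (IRRs) as a potential risk, and 5.1.1 lists hypertension and hypotension among their signs. Protocol 1.3.1 reports three Phase II patients with IRRs. In the PRM-151 group one had dizziness and "another experienced a hypertensive crisis event"; the one placebo patient had two hypertensive crisis events.

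SAP 4.6.5 is short. "Values, along with change from baseline, will be summarized using descriptive statistics for each vital sign parameter", and the summaries "will be presented over time by treatment group". Its baseline rule is "Baseline is defined as the last assessment prior to treatment". The general rule in SAP 4.7.2, which applies unless otherwise specified, is that "the baseline value for each variable will be considered the assessment collected on Baseline Day 1, prior to administration of study drug". Both point to the Day 1 pre-dose reading.

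By contrast, SAP 4.6.4 gives laboratory data shift tables to the worst post-baseline value and the proportion of patients with clinically significant change, and SAP 4.6.6 gives ECGs a shift table.

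**The concern.** Readings at 15-minute intervals around an infusion serve to show what happens around that infusion. The natural reference is the reading taken just before it. SAP 4.6.5 instead refers every reading to Day 1, so a value during the Week 48 infusion is compared with one taken 48 weeks earlier, although a same-visit pre-dose value exists. It does not say how the 15-minute timepoints are handled, and it plans no worst-value or threshold table of the kind laboratory data receive.

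The adverse-event route does not fully fill this gap. Protocol 5.4.5.6 makes a vital-sign abnormality reportable only if it is symptomatic, changes treatment, needs intervention or is judged clinically significant. The IRR definition in SAP 4.6.2 also excludes events judged unrelated. An excursion that meets none of these criteria may appear in no count by arm. Because Phase II had hypertensive events on both arms, a by-arm count from the readings themselves would help separate drug effect from background.

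**Working it through.** The plan states no figure for this analysis, so there is none to reproduce.

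**Inputs from the documents**
- Scheduled infusions: 3 (Days 1, 3, 5) + 12 (Weeks 4 to 48, every 4 weeks) = 15.
- Phase II IRRs: 2/77 = 2.6% on PRM-151 and 1/39 = 2.6% on placebo; 10/111 = 9.0% in the open-label extension.
- Planned patients: 329 per arm.

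**Assumed inputs (not in the documents):** systolic mean 132 mm Hg; SD between patients 14, between visits 8, 11 or 14, within a session 6; four readings per infusion; no drug effect.

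**1. What a mean can show.** Shift in arm mean = share of patients affected × size of rise.
- With 2.6% affected and a rise of 20 to 60 mm Hg: 0.026 × 20 = 0.5 and 0.026 × 60 = 1.6 mm Hg.
- SE of the arm difference = SD × √(2/329). For a change SD of 10 to 20 this is 0.8 to 1.6 mm Hg.
- A mean alone would therefore largely hide rare excursions. A minimum, maximum or count would not.

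**2. SD of change under each reference.**
- Against Day 1: √(2 × between-visit² + 2 × within-session²).
  - Between-visit SD 8: √(128 + 72) = 14.1
  - Between-visit SD 11: √(242 + 72) = 17.7
  - Between-visit SD 14: √(392 + 72) = 21.5
- Against same-visit pre-dose the between-visit term cancels: √(2 × 36) = 8.5.

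**3. If a count of systolic falls above 30% were added.** Simulation under the same assumptions gives the share of infusions flagged by chance. For the Day 1 infusion the two references coincide, so at most 14 infusions per patient are affected: 329 × 14 = 4,606 per arm.

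| Between-visit SD | Flagged against Day 1 | Infusions per arm | Flagged against same-visit pre-dose |
|---|---|---|---|
| 8 | 0.32% | about 15 | at most 0.005% |
| 11 | 1.43% | about 66 | at most 0.005% |
| 14 | 3.58% | about 165 | at most 0.005% |

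The last column is less than one infusion per arm (4,606 × 0.00005 = 0.2). The SAP plans no such count. The table shows only which reference to use if one is added.

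**4. A bare count of systolic below 90 mm Hg.** Under the same assumptions at least one reading falls below 90 in about 1.6%, 2.5% and 3.8% of infusions. No choice of baseline changes that. The pre-dose reading is itself below 90 with probability Φ(−42/√(196 + between-visit² + 36)) = 0.7%, 1.3% and 2.1%. Counting only new values below 90 therefore still leaves at least 0.9%, 1.2% and 1.7% by chance (1.6 − 0.7, 2.5 − 1.3, 3.8 − 2.1). Such a count can be read only against the placebo arm.

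**The case against.** The strongest reply is that the important events are already covered.
- Protocol 4.3.2.1 has the investigator or a designee check Sampson's criteria after every infusion.
- SAP 4.6.2 tabulates all adverse events whatever their causality, suspected IRRs of all grades, and Grade 2 or higher IRRs as events of special interest.
- Possible anaphylaxis is found partly by a standardised MedDRA query and adjudicated blind.
- The Phase II hypertensive crises were themselves found through this route. One of the two patients was on placebo, and none of the IRRs was serious.

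All of this stands. It confines the gap to excursions that are asymptomatic, or not judged clinically significant or related.

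Two stronger readings are tempting and not supported.
- A reader might infer that infusion effects will be averaged away. SAP 4.6.5 says descriptive statistics, not means only, and the list of summary statistics in SAP 4.4.2.1 includes minimum and maximum. A maximum would show a hypertensive crisis, although one extreme per timepoint does not count affected patients.
- A reader might infer that infusion readings are pooled with 48 weeks of drift. No pooling is stated; the handling of these timepoints is simply unspecified. The placebo arm shares any drift, so it adds noise rather than bias.

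Nor does Appendix 5 supply a ready-made cut-off. Its "systolic BP of less than 90 mm Hg or greater than 30% decrease" applies after exposure to an allergen known for that patient, takes the fall from the person's own baseline, and sets no limit for hypertension.

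**Conclusion.** The point holds in a limited form. SAP 4.6.5 uses one Day 1 baseline and specifies no within-infusion analysis of the serial readings, so blood-pressure excursions that the adverse-event route does not pick up may go uncounted by arm. A same-visit reference is better and already collected: under the assumed SDs it reduces the SD of change from 14.1–21.5 to 8.5 mm Hg. The size of that gain rests wholly on the assumed between-visit and within-session SDs. Its direction does not, since any between-visit variation cancels under a same-visit reference.

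This is a cheap improvement to safety reporting. The documents do not support saying that the serial readings are the only objective check on infusion reactions, or that the planned summary must miss them.

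**What to change.** In SAP 4.6.5, as analysis wording only:
- For readings during and after an infusion, take that visit's pre-dose reading as the reference. Keep Day 1 as the baseline for pre-dose readings over time.
- Summarise by arm the largest rise and largest fall per infusion, including upper percentiles and the maximum.
- Report by arm the number of patients and of infusions with a systolic fall above 30% from the same-visit pre-dose reading.
- Show any count of systolic below 90 mm Hg only alongside the pre-dose value, for example as new values below 90 after a pre-dose value of 90 or more.
- State that these are analysis cut-offs, not a diagnosis of anaphylaxis, and that they change no monitoring or treatment rule.

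The cost is a few sentences, one or two extra tables, and a flag for pre-dose readings outside the 60-minute window. No new data are needed.

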4.6.6 ECGs

A shift table of qualitative ECG assessments will be produced.

4.6.7 Other Safety Endpoints

Summaries of safety data by ADA status will be provided as appropriate. See Section 4.7.5 for more details on ADA status.

4.7 OTHER ANALYSES

4.7.1 Summaries of Conduct of Study

Eligibility criteria deviations and other major protocol deviations will be summarized.

The impact of COVID-19 will be assessed by including major protocol deviations related to COVID-19 and by summarizing COVID-19 related intercurrent events by treatment arm.

Compliance analysis will be performed for the overall UCSD-SOBQ and SGRQ questionnaires. Compliance rates will be summarized by number and proportion of patients among those expected to complete the UCSD-SOBQ or SGRQ at each time point.

4.7.2 Summaries of Treatment Group Comparability

Unless otherwise specified, the baseline value for each variable will be considered the assessment collected on Baseline Day 1, prior to administration of study drug.

Demographic and baseline characteristics (including, but not limited to, age, sex, race/ethnicity, concomitant IPF medication use, comorbid illnesses, and pulmonary function) will be summarized overall for the FAS population and by treatment group using descriptive statistics as appropriate.

Compliance with study drug will be computed for each patient as the proportion of prescribed study drug actually taken for the safety population.

Proportions of patients taking each concomitant medication will be provided for the safety population.

Medical history will be summarized using summary statistics, reporting the proportion of patients with at least one medical condition and the total number of medical conditions based on the safety population.

4.7.3 Pharmacokinetic Analyses

Summary tables for plasma concentration of zinpentraxin alfa (mean, standard deviation, %CV, geometric mean, % CV of geometric mean, median, minimum, and maximum) will be produced by visit, treatment arm, and drug generation. As more intensive PK data are collected in patients enrolled in China (and Hong Kong and Taiwan, if applicable) and Japan, summary tables will be produced for these patients separately (see Section 4.7.6 for details on the analyses of China and Japan subpopulations).

Individual patient data and descriptive statistics (i.e., median and interquartile range) will be plotted by visit for each treatment arm.

Exploratory PK analyses to evaluate potential relationships between drug exposure and the efficacy and safety of zinpentraxin alfa will be performed. These analyses will be presented in a separate report and the results will be reported separately as appropriate.

4.7.4 Biomarker Analyses

Exploratory biomarker analyses will be performed to identify and/or evaluate biomarkers in the context of drug activity, efficacy, PK, safety, and/or immunogenicity endpoints. These analyses will be detailed in the Biomarker Analysis Plan and the results will be reported separately.

4.7.5 Immunogenicity Analyses

The following summaries will be provided by the treatment group:

- Number and proportion of ADA-positive patients and ADA-negative patients at baseline (baseline prevalence) and after drug administration (post-baseline incidence)
- Number and percentage of patients with treatment-induced, treatment-enhanced and treatment unaffected ADAs
- Drug concentration at ADA collection timepoints

A by-patient listing of ADA status will be provided.

When determining post-baseline incidence, patients are considered to be ADA positive if they are ADA negative or have missing data at baseline but develop an ADA response following study drug exposure (treatment-induced ADA response), or if they are ADA

positive at baseline and the titer of one or more post-baseline samples is at least 0.60 titer unit greater than the titer of the baseline sample (treatment-enhanced ADA response). Patients are considered to be ADA negative if they are ADA negative or have missing data at baseline and all post-baseline samples are negative, or if they are ADA positive at baseline but do not have any post-baseline samples with a titer that is at least 0.60 titer unit greater than the titer of the baseline sample (treatment unaffected).

The relationship between ADA status and safety, efficacy, and PK, will be analyzed and reported via descriptive statistics. ADA status will also be reported by drug generation.

4.7.6 Analyses of China and Japan Subpopulations

If applicable, a separate analysis will be performed for the China subpopulation, where data from all participants enrolled at sites in mainland China, Hong Kong, and Taiwan (during both the global enrollment phase and the extended China enrollment phase) will be combined and summarized. Similar analysis will be conducted for the Japan subpopulation. These analyses will be detailed in a separate analysis plan. Data from the China extension cohort will not be included in the primary analysis of the main study.

All analyses described in this section will include data from the Japan subpopulation and all data from the China subpopulation collected up to the clinical cutoff date for the China subpopulation analysis as defined in Section 1.2.

The analysis population for the China subpopulation analyses includes all participants enrolled at sites in mainland China, Hong Kong, and Taiwan. The Japan subpopulation includes all participants enrolled in Japan. Data for the China and Japan subpopulations will be analyzed using the same statistical methods as described in Section 4.1 to Section 4.6 when data allow. In addition, key PK and ADA data for the China and Japan subpopulations will be summarized.

The PK parameters for zinpentraxin alfa in plasma will be estimated as appropriate for each subject profile in the China and Japan subpopulations by non-compartmental analysis methods using Phoenix WinNonlin software (v8.3 or later, Certara USA, Inc.).

Plasma PK parameters definitions are as below:

- C_{max} : maximum observed concentration
- T_{max} : time to maximum observed concentration
- AUC_{0-t} : area under the concentration-time curve from hour 0 to the last measurable concentration, calculated using the linear trapezoidal rule for increasing concentrations and the logarithmic rule for decreasing concentrations
- $AUC_{0-\infty}$: area under the concentration-time curve extrapolated to infinity, calculated using the formula:

$$AUC_{0-\infty} = AUC_{0-t} + C_t/\lambda_z$$

where C_t is the last measurable concentration and λ_z is the terminal elimination rate constant

- %AUC_{extrap}: percentage of area under the concentration-time curve that is due to extrapolation from the last measurable concentration to infinity
- λ_z : terminal elimination rate constant, where λ_z is the magnitude of the slope of the linear regression of the log concentration versus time profile during the terminal phase
- $t_{1/2}$: terminal elimination half-life (whenever possible), where $t_{1/2} = (\ln 2)/\lambda_z$
- CL: systemic clearance
- V: volume of distribution

Other parameters may be added as appropriate. PK parameters analysis will use actual times as recorded on the eCRF.

Estimates for PK parameters will be listed and summarized (mean, standard deviation, coefficient of variation mean, geometric mean, coefficient of variation geometric mean, median, minimum, and maximum).

Additional exploratory PK analyses will be conducted as appropriate. Exploratory PK analyses to evaluate potential relationships between drug exposure and the efficacy and safety of zinpentraxin alfa might be described in a separate document and presented in a separate report.

